6.2.20 Patient Global Impression of Change

Patient Global Impression of Change (PGI-C) is a 7-point scale (1 to 7; where 1 corresponds to 'very much improved, 4 is 'no change', and 7 is 'very much worse') that captures the subjects' impression of their overall change since the beginning of the study to specific time points during the study.

For the analysis, subjects will be classified as either responders, that is, a PGIC response of 1 ('very much improved') or 2 ('much improved'), or non-responders, that is, all other PGIC responses (recorded as 3, 4, 5, 6 and 7) at Week 12. Subjects will be classified as non-responders if their PGIC assessments at Week 12 are missing.

6.2.21 Norfolk Quality of Life Questionnaire - Diabetic Neuropathy

The Norfolk Quality of Life Questionnaire – Diabetic Neuropathy (QOL-DN) is a 47-item subject-reported questionnaire designed to measure the relationship between symptomatic diabetic neuropathy and quality of life from the perspective of the subject. It consists of two parts: 1. questions related to symptoms experienced by the patient which has five possible responses ("feet", "leg", "hands", "arms", and "none") and 2. questions related to the impact of patients' neuropathy on activities of daily life in which the responses are in a 5-point Likert scale (0-4; where 0 corresponds to "not a problem" and 4 corresponds to "severe problem"). Further, the questionnaire has five domains: activities of daily living, symptoms, small fiber neuropathy, large fiber neuropathy, and autonomic neuropathy. The QOL-DN total score is calculated as the sum of all the domain scores, which are obtained as follows:

response to the question is "none" then the item score is 0, and 1 otherwise. The symptom domain score is obtained as the sum of the item scores of the seven symptoms questions plus the response to the question "In the past 4 weeks, has the touch of bed sheets, clothes, or wearing shoes bothered you?". Thus, the symptoms domain score is the sum of eight questions in total with a minimum domain score of 0 and maximum domain score of 32.

Activities of daily living: The activities of daily living domain score is obtained by summing the responses to questions 12, 22, 23, 25, and 26 (see below). Thus, the minimum domain score is 0 and maximum domain score is 20.

Question 12: in the past 4 weeks, have you had difficulty doing fine movements with your fingers, like buttoning your clothes, turning pages in a book, picking up coins from a table?

Question 22: in the past 4 weeks, how much difficulty have you had performing the following activities: Bathing/Showering?

Question 23: in the past 4 weeks, how much difficulty have you had performing the following activities: Dressing?

Question 25: in the past 4 weeks, how much difficulty have you had performing the following activities: Getting on or off the toilet?

Question 26: in the past 4 weeks, how much difficulty have you had performing the following activities: Using eating utensils?

Small fiber neuropathy: The small fiber neuropathy domain score is obtained by summing the responses to questions 10, 16, 17, and 18 (see below). Thus, the minimum domain score is 0 and maximum domain score is 16.

Question 10: in the past 4 weeks, have your burned or injured yourself and been unable to feel it?

Question 16: in the past 4 weeks, have you been unable to feel your feet when walking?

Question 17: in the past 4 weeks, have you been unable to tell hot from cold water with your hands?

Question 18: in the past 4 weeks, have you been unable to tell hot from cold water with your feet?

Large fiber neuropathy: The large fiber neuropathy domain score is obtained by summing the responses to questions 8, 11, 13, 14, 15, 24, 27, 28, 29, 30, 33, 34, and 35 (see below) plus the responses to the following questions with the corresponding item scores. Thus, the large fiber neuropathy domain score is the sum of 15 questions in total with a minimum domain score of -4 and maximum domain score of 56.

- "In general, would you say your health now is:"

 Response & item score: Excellent = -2, Very Good = -1, Good = 0, Fair = 1, and Poor = 2
- "Compared with 3 months ago, how would you rate your health in general now?"

 Response & item score: Much Better = -2, Somewhat Better = -1, About the Same = 0,

 Somewhat Worse = 1, Much Worse = 2

Question 8: in the past 4 weeks, has pain kept you awake or woken you at night?

Question 11: in the past 4 weeks, have any symptoms kept you from doing your usual activities during the day?

Question 13: in the past 4 weeks, have you felt unsteady on your feet when you walk?

Question 14: in the past 4 weeks, have you had any problem getting out of a chair without pushing with your hands?

Question 15: in the past 4 weeks, have you had a problem walking down stairs?

Question 24: in the past 4 weeks, how much difficulty have you had performing the following activities: Walking?

Question 27: in the past 4 weeks, have you had any of the following problems with your work or other regular daily activities as a result of your physical and emotional health: Cut down on the amount of time you spent on work or other activities?

Question 28: in the past 4 weeks, have you had any of the following problems with your work or other regular daily activities as a result of your physical and emotional health: Accomplished less than you would like?

Question 29: in the past 4 weeks, have you had any of the following problems with your work or other regular daily activities as a result of your physical and emotional health: Were limited in the kind of work or other activities you could perform?

Question 30: in the past 4 weeks, have you had any of the following problems with your work or other regular daily activities as a result of your physical and emotional health: Had difficulty performing the work/other activities (it took extra effort)?

Question 33: in the past 4 weeks, to what extent has your physical health interfered with your normal social activities with family, friends, neighbors, or groups?

Question 34: in the past 4 weeks, how much did pain interfere with your normal work (including work both outside the home and housework)?

Question 35: in the past 4 weeks, how much did weakness or shakiness interfere with your normal work (including work both outside the home and housework)?

Autonomic neuropathy: The autonomic neuropathy domain score is obtained by summing the responses to questions 19, 20, and 21 (see below). Thus, the minimum domain score is 0 and maximum domain score is 12.

Question 19: in the past 4 weeks, have you had a problem with vomiting, particularly after meals (but not due to flu or other illness)?

Question 20: in the past 4 weeks, have you had a problem with diarrhea and/or loss of bowel control?

Question 21: in the past 4 weeks, have you had a problem with fainting or dizziness when you stand?

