### 9.2.3. Norfolk Quality of Life Questionnaire – Diabetic Neuropathy (QOL-DN)

The Norfolk QOL-DN is a 47-item, subject-reported questionnaire designed to measure the relationship between symptomatic diabetic neuropathy and quality of life from the perspective of the patient. It is composed of 2 parts: questions related to symptoms experienced by the patient and questions related to the impact of the patient's neuropathy on activities of daily life. A factor analysis performed on the Norfolk QOL-DN separated the questions into 5 domains: activities of daily living, symptoms, small fiber neuropathy, large fiber neuropathy, and autonomic neuropathy. The QOL-DN is sensitive to the different features of diabetic neuropathy including small fiber, large fiber, and autonomic nerve function [Vinik 2005]. Aptinyx Confidential Page 48 of 74

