6.11.2.3 Percentage of subjects achieving ≥30% and ≥50% reduction from baseline in the weekly mean NRS average pain intensity related to DPN at Week 12

Percentage of subjects achieving both $\geq 30\%$ and $\geq 50\%$ reduction from baseline in the weekly mean NRS average pain intensity related to DPN at Week 12 will be analyzed and presented as described in Section 6.11.2.2.

6.11.2.4 Change from baseline to Week 12 in Norfolk Quality of Life Questionnaire – Diabetic Neuropathy score

A similar approach in modeling the REML-based MMRM as in the primary analysis will be applied to the change from baseline to Week 12 in the QOL-DN total score except that the outcome variable will be change from baseline to Weeks 4 and 12 in the QOL-DN total score, and the fixed effects are as follows: site, treatment group, week, baseline QOL-DN total score, and treatment-by-week interaction as terms in the model.

Observed QOL-DN total scores at baseline and at each week (4 and 12), as well as the change from baseline QOL-DN total scores at each week (4 and 12) will be presented by treatment group. The LS means, corresponding SEs, and 95% CIs for each treatment group will also be presented at each week (4 and 12). Additionally, estimate, corresponding SE, and p-value of the treatment difference at Week 12 will also be presented.

Listing of the QOL-DN individual item scores, as well as the domain scores at baseline and at Weeks 4 and 12 will be presented.

6.11.2.5 Use of rescue medication, including the proportion of subjects using rescue medication, the frequency and amount used

The total number of tablets taken and percentage of rescue-free days per week will be summarized by treatment group.

The proportion of subjects that used rescue medication (one or more tablets) at any point after the first dose of study drug will also be summarized by treatment group. A Z-test on equality of two proportions will be performed to compare the treatment groups, using the following SAS code:

```
PROC FREQ DATA=DATIN ORDER=DATA;
    TABLES TREATMENT*RESPONDER / RISKDIFF(EQUAL VAR=NULL CL=WALD);
    ODS OUTPUT PDIFFCLS = DIFF PDIFFTEST = PVAL;
RUN;
```

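### SAP 6.2.17.3 sets responder cut-offs of -30 and -50 on a raw NRS change that cannot go below -10; separately, and less certainly, the readable QOL-DN symptom rule gives a maximum of 11 against a stated 32

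*SAP*

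**What the plan says.** **Responder definition.** SAP 6.2.17.3 classifies a subject as a responder at Week 12 if the percent reduction in average DPN pain reaches 30%, and separately 50%. Each definition carries a parenthetical programming note that puts the change from baseline at or below -30, or -50. SAP 6.2.14 defines change from baseline as the post-baseline value minus the baseline value. SAP 6.2.15 defines percent change as a separate quantity: that difference times 100, divided by baseline. SAP 6.2.17.2 closes by deriving both quantities for the NRS. Both responder rates are secondary endpoints (SAP 3.2, 6.11.2.3).

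**QOL-DN symptom domain.** SAP 6.2.21 says that the symptom part "has five possible responses ('feet', 'leg', 'hands', 'arms', and 'none"). The surviving part of the scoring sentence reads "response to the question is 'none' then the item score is 0, and 1 otherwise". The domain is then "the sum of the item scores of the seven symptoms questions plus the response to the question" about the touch of bed sheets, clothes or shoes, and the SAP describes it as "the sum of eight questions in total with a minimum domain score of 0 and maximum domain score of 32". The QOL-DN total is the sum of five such domains. In SAP 6.11.2.4, "the outcome variable will be change from baseline to Weeks 4 and 12 in the QOL-DN total score".

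**The concern.** In 6.2.17.3 the note addressed to the programmer names a variable that cannot reach the cut-offs attached to it. It also disagrees with the words around it, which speak of percent reduction. Taken literally, it would leave both responder endpoints with no responders at all.

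In 6.2.21 the item rule and the stated range do not agree as far as the text can be read. The rule fixes how many points symptoms can contribute to the QOL-DN total, which is a tested secondary endpoint. SAP section 9, item 6, also adds the domain scores as an efficacy endpoint, and 6.11.2.4 promises: "Listing of the QOL-DN individual item scores, as well as the domain scores at baseline and at Weeks 4 and 12 will be presented". A reader of those outputs needs to know which scoring was applied.

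**Working it through.** **1. Responder cut-offs**

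Inputs: NRS range 0 to 10 (Protocol 9.2.1, SAP 6.2.17); change = post - baseline (SAP 6.2.14); percent change = change x 100 / baseline (SAP 6.2.15); cut-offs -30 and -50 (SAP 6.2.17.3).

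- Baseline and weekly means both lie between 0 and 10, so the smallest possible raw change is 0 - 10 = -10.
- -10 is greater than -30 and greater than -50. No possible pair of scores meets either cut-off on the raw scale.
- On the percent scale the same best case is (0 - 10) x 100 / 10 = -100, which meets both.
- Even at the highest possible baseline of 10, a 30% reduction is a raw change of -0.30 x 10 = -3, and a 50% reduction is -0.50 x 10 = -5. Cut-offs of -30 and -50 therefore make sense only for percent change.

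**2. QOL-DN ranges**

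The control comes first. With 0-4 items, and the two general-health items running from -2 to 2, the four other domains in SAP 6.2.21 reproduce:

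| Domain | Arithmetic for the maximum | Stated range |
|---|---|---|
| Activities of daily living | 5 x 4 = 20 | 0 to 20 |
| Small fiber | 4 x 4 = 16 | 0 to 16 |
| Large fiber | 13 x 4 + 2 x 2 = 56; minimum 2 x (-2) = -4 | -4 to 56 |
| Autonomic | 3 x 4 = 12 | 0 to 12 |

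The SAP describes the large fiber domain as "the sum of 15 questions in total with a minimum domain score of -4 and maximum domain score of 56", which matches.

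The symptom domain depends on the reading. The bed-sheets question is taken as 0-4 throughout. That is an assumption: the SAP gives this scale for the part 2 questions and does not repeat it for this one.

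| Reading | Maximum |
|---|---|
| 0/1 per question, as readable | 7 x 1 + 4 = 11 |
| One point per site, several sites selectable | 7 x 4 + 4 = 32 |
| One point per site, only one site selectable | 7 x 1 + 4 = 11 |
| All eight questions 0-4 | 8 x 4 = 32 |

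Consequence for the total: the other four maxima sum to 20 + 16 + 56 + 12 = 104. The total then has a maximum of 104 + 32 = 136 under the stated range, or 104 + 11 = 115 under the readable rule. The minimum is -4 in both cases. Symptoms make up 32/140 = 22.9% of the span in the first case and 11/119 = 9.2% in the second.

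The item count does not decide between the readings. Protocol 9.2.3 says "The Norfolk QOL-DN is a 47-item, subject-reported questionnaire". The scored items outside the seven symptom questions number 5 + 4 + 15 + 3 + 1 = 28. Adding 7 gives 35, and adding 7 x 4 gives 56. Neither is 47.

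**The case against.** **On the responder note.** The same sentence already says percent reduction. The next section (6.2.17.4) derives its percent reductions by explicit reference to 6.2.15. A programmer would almost certainly use the right variable, and a responder table with zeros in both arms would be noticed at once. That stands as an argument about likelihood. It does not remove the contradiction, because the parenthesis is the part written as the programming rule and the SAP gives the term it uses a different meaning. A reader might infer that the responder results will be wrong. The documents do not support that; they show only that the instruction as written cannot work.

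**On the QOL-DN range.** The strongest reply is that the rule is damaged in the text available for review. The domain heading and the start of the scoring sentence are missing, and the lost words are those that would say whether the 0/1 score applies to each question or to each body site. Four sites plus one 0-4 question give exactly 32, and the SAP's other four ranges are right. All of this stands, and it rules out a finding that the plan is wrong. What remains is that the surviving clause turns on whether the answer is 'none', not on how many sites are ticked. The readable text also does not say whether several sites may be chosen, and 32 also arises from 8 x 4.

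Three stronger readings are tempting and should not be drawn:

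- **That 32 is an error.** The missing words could make rule and range agree.
- **That independent programming (SAP 6.3.3) would miss the problem because both programmers code the same sentence.** They work from the intact SAP and from dataset specifications held in a separate document (SAP 6.3.2), so the documents do not show this.
- **That individual scores would shift by up to 32 - 11 = 21 points.** That gap requires several sites to be selectable and all four to be reported for all seven symptoms. It is zero if each symptom is reported at one site.

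**Conclusion.** **Responder note: holds, on intact text.** The variable named in SAP 6.2.17.3 has a floor of -10 and cannot meet cut-offs of -30 or -50. Taken literally, the rule gives zero responders on two secondary endpoints. The only assumption is that the term carries its 6.2.14 meaning. The intended meaning is clear from the surrounding sentence, so this is a wording error in a programming instruction and not a flaw in the endpoint.

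**QOL-DN symptom domain: an open query, held with lower confidence.** The readable rule gives a maximum of 11 against a stated 32, and a total maximum of 115 against 136. This rests on a 0-4 bed-sheets question and on reading the surviving clause as one score per question. The mismatch is confined to this domain. Because the sentence is incomplete in the text available, it shows a need to check, not an error.

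Neither point touches the primary analysis. For the QOL-DN scoring, no effect on the treatment estimate or a p-value can be derived from the documents.

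**What to change.** 1. In SAP 6.2.17.3, in both programming notes, name the percent change defined in Section 6.2.15 as the variable tested against -30 and -50. This is a substitution of a few words in two places. It costs nothing and needs no new data.
2. In SAP 6.2.21, check the symptom rule on the intact page and against the instrument's scoring instructions.
   - If the intact page already gives a rule consistent with 0-32, no change is needed.
   - If it gives a single 0/1 score per question, correct whichever of rule or range departs from the instrument. Either state how a symptom question can score up to 4 (including whether several sites may be selected) and keep 32, or keep the 0/1 rule and change the maximum to 11.
   - State the scale of the bed-sheets question at the same time.

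The cost is one look-up and at most a one-line correction. Both are best settled before unblinding, so that the scoring is not chosen with results in view. The documents do not show whether unblinding has taken place.

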6.2.22 Brief Pain Inventory for Diabetic Peripheral Neuropathy

The Brief Pain Inventory for Diabetic Peripheral Neuropathy (BPI-DPN) is a patient-completed numerical rating scale that assesses the severity of pain (Severity scale), it's impact on daily functioning (Interference scale), and other aspects of pain (location of pain, relief from medications, etc.). The Severity scale which consists of 4 items (Worst, Least, Average, Pain now) uses a 0 to 10 numeric rating scale for each item where 0 corresponds to "no pain" and 10 corresponds to "pain as bad as you can imagine". Moreover, the Interference scale which consists of 7 items (General Activity, Mood, Walking Ability, Normal Work, Relations with Others, Sleep, Enjoyment of Life) also uses a 0 to 10 numeric rating scale for each item where 0 corresponds to "does not interfere" and 10 corresponds to "completely interferes".

The Pain Severity index, which is the average of all items of the Severity scale, will be obtained as long as all items in the Severity scale have a reported score. Otherwise, it will be set to missing.

Similarly, the Pain Interference index which is the average of all items of the Interference scale, will be obtained as long as at least 4 items in the Interference scale have a reported score. Otherwise, it will be set to missing. These are the composite scores of interests. No BPI-DPN total score will be calculated

6.2.23 Pain Catastrophizing Scale

The Pain Catastrophizing Scale (PCS) is a comprehensive evaluation instrument that encompasses different perspectives on catastrophizing and assesses the state of mind of patients in pain. The PCS has 13 items which are statements describing different thoughts or feelings that may be

associated with pain. Each item has a response on a 5-point Likert scale (0-4; where 0 corresponds to "not at all" and 4 corresponds to "all the time") which reflects the degree of the subject's thoughts and feelings when experiencing pain.

The PCS total score (which ranges from 0 to 52) is calculated by summing responses to all 13 items. PCS subscale scores can be obtained as follows: Rumination (sum of items 8, 9, 10, 11); Magnification (sum of items 6, 7, 13); Helplessness (sum of items 1, 2, 3, 4, 5, 12).

For this study, item 7 was not recorded, therefore a modified PCS score (sum of the 12 remaining items, ranging from 0-48) will be calculated. The Rumination and Helplessness subscale scores will be calculated as described; however, the Magnification subscale score will be omitted from the analysis.

Pain Catastrophizing Scale (PCS) – 13 Items

- Item 1: Worry Whether the Pain Will End
- Item 2: Feel I Can't Go
- Item 3: Terrible- Think Never Get Better
- Item 4: Pain Overwhelms Me
- Item 5: Can't Stand it Anymore
- Item 6: Afraid the Pain Will Get Worse
- Item 7: Thinking of other Painful Events [Not Recorded for This Study]
- Item 8: Anxiously Want Pain to Go Away
- Item 9: Can't Seem to Keep Out of Mind
- Item 10: Keep Thinking How Much It Hurts
- Item 11: Keep Thinking- Want Pain to Stop
- Item 12: Nothing Reduces Intensity of Pain
- Item 13: Wonder Something Serious Happen

6.2.24 Sheehan-Suicidality Tracking Scale

The standard version of the Sheehan-Suicidality Tracking Scale (S-STS) is a 16-item scale that assesses the seriousness of suicidality phenomena on a Likert-type scale (0 to 4; where 0 corresponds to "not at all" and 4 corresponds to "extremely"). It also assesses the frequency of key phenomena and the overall time spent in suicidality. The total S-STS score is obtained by summing the responses to:

- question 1a (only if the answer to question 1b: did you intend to die as a result of any accident? is "Yes")
- questions 2 to 11
- max of responses to question 12 or any row of question 16
- max of responses to question 14 or any row of question 15

Question 1a: how seriously did you plan or intend to hurt yourself in any accident, either by not avoiding a risk or by causing the accident on purpose?

Question 2: think (even momentarily) that you would be better off dead, need to be dead or wish you were dead?

Question 3: think (even momentarily) about harming or hurting or injuring yourself—with at least some intent or awareness that you might die as a result—or think about suicide (killing yourself)?

Question 4: have a voice or voices telling you to kill yourself or have dreams with any suicidal content?

Question 5: have any suicide method in mind (i.e., how)?

Question 6: have any suicide means in mind (i.e., with what)?

Question 7: have any place in mind to attempt suicide (i.e., where)?

Question 8: have any date / timeframe in mind to attempt suicide (i.e., when)?

Question 9: intend to act on thoughts of killing yourself?

Question 10: intend to die as a result of a suicidal act?

Question 11: feel the need or impulse to kill yourself or to plan to kill yourself sooner rather than later?

Question 12: take active steps to prepare for a suicide attempt in which you expected or intended to die (include anything done or purposely not done that put you closer to making a suicide attempt)?

Question 14: attempt suicide (try to kill yourself)?

Question 15: Since your last visit, how many times did you attempt suicide?

Question 16: Since your last visit, how many times did you take active steps to prepare for a suicide attempt in which you expected or intended to die (include anything done or purposely not done that put you closer to making a suicide attempt)?

